MedStar Diabetes Pathway Ongoing Chart Review Protocol

[name] Principal Investigator

Sub-Investigators

[name] [name]

[name], CRNP, CDE

[name], CRNP

[name]

[name], MS, RD, CDE and [name], MS, RD, CDE
Program Managers

June 1.2016

MedStar Diabetes Pathway Ongoing Chart Reviews

I- Background.

The MedStar Diabetes Pathway (MDP) early pilot program has generated evidence that an innovative technology-enabled “Boot Camp” approach to the delivery of diabetes survival skills education and medication management has a significant impact on glycemic control and healthcare utilization measures. The MDP is a 12 week Diabetes “Boot Camp” technology-enabled intervention which will offer learner-centered survival skills self-management education (DSSE) and algorithm-driven diabetes medications (DM) titration by Endocrinologist-supervised Certified Diabetes Educators (CDE), NPs and PharmDs. The program has been offered at 5 MedStar Medical Group (MMG) Primary Care Practices in FY 15-16 to high risk adults with uncontrolled type 2 diabetes who have a hemoglobin A1C (A1C) level -a marker of average blood glucose (BG) levels in the 2-3 months prior to the time the test is done- which is at or above 9% - considered to be poor control, and 1 or more additional risk factors for poor health outcomes. The program has been well received by MedStar Primary Care Providers and their diabetes patients.

Patients who consent to join the program attend two 1:1 visits with a CDE followed by “virtual” visits via telephone/texting. DSSE is tailored to baseline DM knowledge and medication adherence deficits. An FDA cleared cellular-enabled blood glucose (BG) monitoring system (Telcare BGM®) auto- transmits BGs to a provider dashboard in near-real-time. The CDE reviews BGs and contacts patients at minimum weekly to discuss and make adjustments to DM medications and/or lifestyle, until BG targets are reached. The patient then returns to his/her Primary Care Provider (PCP) with any further ongoing DM management recommendations.

Ninety-eight (98) patients with uncontrolled type 2 diabetes have completed the MedStar Diabetes Pathway Boot Camp. A1C, a measure of average blood glucose control over the 2-3 months prior to the test being done, was checked at baseline and then after 3 months follow-up. Admissions and resource utilizations were measured for the period 6 months before baseline and then recorded between baseline and 3 months and between 3 months and 6 months. For comparison of A1C improvement, patients were matched to controls at a 1:3 ratio on age, sex, race/ethnicity, insurance group, and baseline A1C. The difference in improvements of A1c between a case and its matched control was tested. Utilization has not yet been captured for controls.

Clinical and Health Resources Utilization Outcomes.

- **A1C Performance.**

Blood glucose control improvement, as measured by change in A1C results is shown below.

Table 1: Change in A1C

	Boot Camp Cases	Control Cases	P value
Baseline A1C (%)	11.35 (1.86)	11.41 (1.71)	0.439
3 month A1C (%)	8.31 (1.52)	9.77 (1.98)	<0.001
Change in A1C (%)	-3.08 (2.01)	-1.64 (1.97)	<0.001
Percent A1C lowering	27%	14%	

The 3.08 % lowering of A1C among Boot Camp patients is highly clinically important. In comparison, most drug trials where A1C lowering is measured, there is typically reduction in A1C of 0.5-1.5% depending upon the drug or drugs being tested¹. Furthermore, a 1% absolute reduction in A1C can be correlated with an approximately 15% reduction in risk for myocardial infarction². The fact that lowering in A1C was also seen among control cases is not completely unanticipated. Per current standard care, when a patient presents with a markedly elevated A1C the physician caring for him/her would implement measures to help improve control which explains the concurrent fall in A1C over time. These results show that the Boot Camp intervention effectively doubled A1C lowering when compared to controls.

- **Health Resource Utilizations.**

Utilization for urgent care visits, urgent PCP visits, hospitalizations, and Emergency Department (ED) visits due to diabetes, taken in the 6 months before the listed time is shown in Table 2.

Table 2. Health Resource Utilizations

	Baseline (n)	3 months		6 months		P value
	Number	Number	% Reduction	Number	% Reduction	
Urgent Care Visits	3	0		0		0.109
Urgent PCP Visits	13	1	91%	1	92%	0.002
Hospitalizations	9	1	88%	3	66%	0.207
ED Visits	18	1	94%	2	88%	<0.001

There is an association between time and urgent PCP visits and ED visits. This means that for those patients enrolled in the program there appears to be a reduction over time in urgent PCP visits and ER visits following program completion. The number of hospitalizations was low overall and does show a trend for reduction over time.

Summary of Findings.

This pilot evidence demonstrates a significant impact on glycemic control and healthcare utilization measures as the result of a concise, focused DM education and medication management intervention.

Phase 2.0 MedStar Diabetes Pathway Expanded Pilot

Building on the success of the MDP Phase 1.0 pilot, the next steps in expanding the program will be as follows:

- **Transition** of the Pathway from early feasibility pilot to the next phase as an expanded pilot program integrated within the MedStar Health System care delivery network and built upon a sustainable infrastructure (brick and mortar –plus- virtual components) across early adopter MMG practice sites.
- **Expand recruitment** to include high risk patients with uncontrolled type 2 diabetes, including those with a new diagnosis and A1C >9%, who have MedStar Emergency Department and/or Inpatient encounters
- **Spread** to additional targeted MedStar Medical Group (A&B) Primary Care Practices and/or to MedStar Managed Care Plan participants (MedStar Family Choice, MedStar Select)

As the MDP is transitioning into a clinical program offered at various MedStar sites, the MDP clinical team is reviewing the data collected during the pilot to improve the program and adapt it to various clinical settings in order to better serve the target patient population. It will be imperative to continue reviewing patient clinical outcomes as the program expands in order to insure continuous quality improvement of the program. This will be achieved through chart reviews of patients receiving diabetes care via the MDP.

III- Chart Review and Data Collection

MDP patients' chart review:

MDP target population:

Inclusion Criteria

- Active and established patient of a MedStar Medical Group Ambulatory Primary Care practice provider:
- Diagnosis of type 2 diabetes on EMR problem list for ≥ 1 year
- New diagnosis of type 2 diabetes with $A1C \geq 9$
- Active practice patient as evidenced by one or more visits to PCP in the past 12 months
- Age ≥ 21 to < 75 years
- $A1C \geq 9.0\%$ at their last visit to MedStar Medical Home, ED or hospital admission.
- Primary Care Provider willing to have patient enter the program
- Patient is able and willing to participate in the program
- Proficient in English

-AND- one or more of the following high risk characteristics:

- Acute care encounter(s) including) ED visit(s) or hospital admission(s) in the past year with uncontrolled diabetes (BG > 200mg/dL or A1C >9%; severe hypoglycemia = BG <40mg/dL requiring assistance to treat)
- Evidence of low medication adherence as evidenced by no refills since one or more prescribed DM RXs “ran out” (based on last Rx for each DM med and time period was prescribed for on EMR/SureScripts medications list); or any other circumstance that has

been identified by the health care team which indicates poor adherence to prescribed medication.

- Does not meet HEDIS diabetes measures for two or more of: no MA/Cr, no DM retinal exam, no lipid profile
- SBP \geq 140 mmHg
- LDL \geq 100 mg/dL
- Depression diagnosis on problem list (*or depression medication on med list*)
- BMI >32

Exclusion Criteria

- Known history of DKA
- No MedStar PCP visit within past 12 months
- Endocrine or Diabetes Education consult referral order in the past 6 months which resulted in Endo visit(s) or DSME visit(s) documented in chart or self-reported by patient during initial screen
- Active additional medical issues which in the opinion of the care team would preclude concentrating on BG control and/or would predispose to ED visits and/or hospital admits independent of glycemic control, e.g.: severe CHF, severe COPD; severe mental illness.
- Resident of skilled nursing facility, nursing home or receiving home health care services.
- Active cancer in the preceding 3 years excluding nonmalignant basal cell cancer
- Supraphysiologic doses of glucocorticoids (hydrocortisone > 30mg/day; prednisone > 5-6mg daily; dexamethasone > 2mg daily).
- Pregnant or anticipates attempting conception in the following year
- Patient and/or custodial caregiver unwilling and/or unable to participate in program-related activities

The following data will be collected retrospectively from the charts of patients that complete the MDP.

- Demographics
- A1C baseline, at 3 month after baseline visit to assess impact of the pathway.
- Hypoglycemic events (BG<70 and <40) during the 6 months of enrollment in MDP
- Diabetes 2 go Knowledge test
- ED and hospital visits in 30 days and 90 days prior to and after the boot camp
- Referring MedStar Provider satisfaction with intervention
- Patient satisfaction with the MDP

In addition, the clinical team will also compare the clinical and utilization outcomes of patients enrolled in the MDP with those of a randomly selected control group consisting of MedStar

patients with elevated A1C levels. This will be done to allow a better assessment of the impact and effectiveness of the MDP.

Once the data is obtained, it will be de-identified prior to data analysis and reporting. Demographics will be reported as a group, i.e. percentage of patients within a certain age group or geographic area or with a certain type of insurance to insure equal access to the MDP, and help recruit underrepresented groups so they can also benefit from the program.

Data Management

The MedStar Health Research Institute will provide data management services for all aspects of the chart review process, including preparation of the program REDCap database, quality checks of data and developing processes for bringing data into REDCap from available data sources held by system partners which will be leveraged for the program. All data will be de-identified prior to presentation to the Biostatistician for analysis.

Data Analysis and Reporting Plan

Data analysis will be performed by the MHRI Biostatistician. All data will be de-identified prior to submission to the biostatistician for analysis. Results will be reviewed for quality improvement purposes and will also be presented at national meetings. Additionally, one or more manuscripts will be prepared for submission to peer-reviewed journals.

References

1- Management of Hyperglycemia in Type 2 Diabetes: A Patient-Centered Approach

Position Statement of the American Diabetes Association (ADA) and the European Association for the Study of Diabetes (EASD). [Silvio E. Inzucchi](#), MD,¹ [Richard M. Bergenstal](#), MD,² [John B. Buse](#), MD, PHD,³ [Michaela Diamant](#), MD, PHD,⁴ [Ele Ferrannini](#), MD,⁵ [Michael Nauck](#), MD,⁶ [Anne L. Peters](#), MD,⁷ [Apostolos Tsapas](#), MD, PHD,⁸ [Richard Wender](#), MD,⁹ and [David R. Matthews](#). Diabetes Care. 2012 Jun; 35(6): 1364–1379.

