Statistical Analysis for the MedStar Diabetes Pathway Ongoing Chart Review Protocol. (June 1, 2016).

The study was powered to detect a difference of 0.5 in the change in HbA_{1c} with SD=2 with 80% power at alpha=0.05 with a sample size of 128 in each group (paired t-test). The study reaches 100% power to detect this observed difference (1.6, SD=2.25, post-hoc) with an alpha level of 0.01. Data were summarized using means and standard deviations for continuous variables and frequencies and percentages for categorical variables. Differences in patient characteristics and the unadjusted differences in the outcome measures between the intervention and control groups were tested using linear mixed models, McNemar tests, and conditional logistic models due to matching (Tables 2 and 3). The significance of the comparison between the groups of their respective within group risk change from pre to post-intervention was determined by longitudinal Poisson models that include time and group interactions. Multivariable Poisson regression models adjusted for pre-intervention utilization, baseline HbA_{1c}, age, and sex were used to estimate post-intervention 30-day and 90-day hospital admission and ED visit risk for participants compared to controls (Table 3). The average decrease in HbA_{1c} among men compared to women was examined using a mixed model that included an interaction with sex and group.

Pre-intervention differences between the groups in utilization outcomes were computed and tested using unadjusted Poisson regression models. Analyses were conducted in R 3.1.0 (R Core, Vienna, Austria) (31) and Stata 14 (StataCorp, College Station, TX) (32).

We also conducted an analysis to examine potential for monetization of the intervention benefits from reduced inpatient services to the health system. Based on the expected times of hospitalization per patient in 90 days for both the intervention group and comparison group, estimated by the Poisson regression model, we projected the annual difference in usage of inpatient services between a patient with and without the intervention. The projected change in usage was then multiplied by the expense per diabetes associated hospitalization, which was calculated from the actual claims data of the health system's employee health plan in Year 2017 to be \$25,162.95 per hospitalization.

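### For patients recruited through an ED visit or admission shortly before the boot camp, that encounter is counted in the pre-period, which biases the pre-to-post utilization result in the programme's favour by an unknown amount

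*Protocol*

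**What the plan says.** The Protocol, under Phase 2.0, extends recruitment to high-risk patients with uncontrolled type 2 diabetes "who have MedStar Emergency Department and/or Inpatient encounters". Under Inclusion Criteria, the qualifying A1C may be the one taken "at their last visit to MedStar Medical Home, ED or hospital admission". One of the seven high-risk characteristics, of which at least one is required, is "ED visit(s) or hospital admission(s) in the past year with uncontrolled diabetes".

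The data list in section III collects "ED and hospital visits in 30 days and 90 days prior to and after the boot camp". Neither the Protocol nor the SAP removes the recruiting encounter from the pre-period count, sets a washout, or records how the patient was recruited.

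The comparison group in section III is a "randomly selected control group consisting of MedStar" patients with elevated A1C. No acute encounter is required of them. In the pilot (section I), patients were "matched to controls at a 1:3 ratio on age, sex, race/ethnicity, insurance group, and baseline A1C"; prior utilization is not on that list.

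The SAP tests the "comparison between the groups of their respective within group risk change from pre to post-intervention" by "longitudinal Poisson models that include time and group interactions". Separately, it fits Poisson models for post-period admissions and ED visits at 30 and 90 days, adjusted for pre-intervention utilization, baseline HbA1c, age and sex. It also tests pre-intervention utilization differences between the groups.

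**The concern.** For some programme patients, one event does two jobs: it brings them into the programme, and it is counted in the baseline of the outcome. A patient identified at an ED visit two weeks before starting cannot have a pre-count of zero but can easily have a post-count of zero. The disappearance of the recruiting visit then reads as a programme effect.

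The control group does not cancel this, because controls are sampled on A1C and carry no forced event. The interaction therefore inherits the same bias as the plain within-programme change.

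The stakes are real. The Protocol's summary of the pilot already reads an uncontrolled fall in utilization as the result of the intervention, and the Phase 2 results are meant for national meetings and journals.

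**Working it through.** **Plan's own figures.** The documents give no power or sample size for utilization. The SAP's only sample size, 128 per group for a difference of 0.5 in HbA1c change (SD 2, 80% power, alpha 0.05, paired t-test), reproduces: 128 pairs give power 0.8015 (two-sided), and 127 give 0.7984. This point does not affect it.

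**Inputs.**
- Background rate λ per patient per window. Protocol Table 2 gives 18 diabetes-related ED visits in 98 patients over 6 months. For 90 days, 18/98 × 90/182 = 0.091. For 30 days, 18/98 × 30/182 = 0.030.
- A second λ of 0.30 per 90 days. This is an assumption. The Phase 2 count is not restricted to diabetes-related visits, so its background rate may exceed the pilot's.
- q, the share of programme patients whose recruiting encounter falls inside the window. The documents do not give it; a range is assumed.

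**Formula.** With no programme effect, and other visits occurring at the same rate before and after, the expected pre-count is λ + q and the expected post-count is λ. The apparent fall is q/(λ + q).

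| q | λ = 0.091 (pilot ED rate) | λ = 0.30 (assumed) |
|---|---|---|
| 5% | 0.05/0.141 = 35% | 0.05/0.35 = 14% |
| 10% | 0.10/0.191 = 52% | 0.10/0.40 = 25% |
| 20% | 0.20/0.291 = 69% | 0.20/0.50 = 40% |

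**30-day window.** Here q must be the share recruited within 30 days. If 20% of patients were recruited within 30 days, the fall is 0.20/0.230 = 87%. If 20% were recruited within 90 days, spread evenly, then q for 30 days is 6.7% and the fall is 0.067/0.097 = 69%.

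**Does the interaction remove it?** Trials with no programme effect were simulated: 128 per group, 600 runs per setting, overdispersed counts, λ of 0.091 (ED) or 0.136 (ED plus admissions, 27/98 × 90/182), and controls without a recruiting event. The interaction was fitted with standard errors clustered by patient. The post-period model adjusted for pre-count only. Two cases were run: recruits carry a persistently higher visit rate, or they do not. Ranges cover both values of λ and, for the interaction, both cases.

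| q | Interaction rate ratio | False findings of benefit, interaction (nominal 2.5%) | Adjusted post-period ratio, recruits at higher rate | Adjusted post-period ratio, recruits not at higher rate |
|---|---|---|---|---|
| 0 | 0.99–1.01 | 2–3% | 0.97–1.04 | 0.99–1.00 |
| 10% | 0.48–0.59 | 22–29% | 1.00–1.07 | 0.94–0.95 |
| 25% | 0.25–0.40 | 59–72% | 1.02–1.05 | 0.87–0.88 |
| 50% | 0.15–0.28 | 87–94% | 1.02–1.07 | 0.77–0.81 |

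Taking the recruiting encounter out of the pre-count removes the q term from the formula, so the expected no-effect ratio returns to 1.00.

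**The case against.** The strongest reply is about reach. A reader might infer that every programme patient's utilization must fall by construction. The documents do not support that. An acute encounter is one of seven alternative high-risk characteristics and looks back a year, whereas the outcome windows are 30 and 90 days. The qualifying A1C may come from the Medical Home, and the Protocol gives no interval between encounter and start. Only patients whose recruiting encounter falls inside the window are affected. This stands, and it is why the size is given as a range in q.

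A reader might also infer that the forced event, entering as a covariate, pushes the adjusted post-period ratio in the programme's favour. That holds only if the recruiting visit does not mark a persistently higher rate. If it does, the simulated ratio is about 1.0 or slightly above. The direction cannot be settled from the documents.

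The illustrated falls depend on the background rate. The pilot rate covers diabetes-related visits only, and recruits may be heavier users than average; either would shrink the percentage. On the other side, the pilot baseline may itself contain qualifying encounters, so the underlying rate could be lower and the artefact larger.

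The SAP also tests baseline utilization differences, so an excess in programme patients may be seen. Seeing it does not remove it from the interaction.

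Finally, the problem is not wholly separate from the choice of controls. Controls with a comparable index encounter and the same clock start would put the artefact in both groups of the interaction. The within-programme fall would still be distorted.

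**Conclusion.** The concern holds for the pre-to-post contrasts. Followed as written, the plan counts the recruiting encounter whenever it falls in the window, so the within-programme fall and the time-by-group interaction are biased in the programme's favour. This is more than a missing detail, because the stated count includes the encounter and the stated test does not offset it.

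The size is unknown because q is not given. Over q = 5% to 20%, the spurious 90-day fall runs from 14% to 40% at an assumed rate of 0.30, and from 35% to 69% at the pilot ED rate. These figures assume no programme effect, one recruiting visit per affected patient, and a stable rate of other visits.

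The conclusion does not extend to the HbA1c analysis. The adjusted post-period model is much less affected, and any bias there depends on whether the recruiting visit marks a lasting difference in rate.

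**What to change.** In the Protocol's section III data list, add recruitment source and the date of the recruiting encounter.

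In the SAP:
- For the pre-to-post Poisson models, exclude the recruiting encounter from programme patients' 30- and 90-day pre-counts. Randomly selected controls have none to exclude, and the SAP should say so.
- Report the pre-to-post result with and without this exclusion, and by recruitment route (primary care versus ED or inpatient).
- Base the utilization effectiveness statement on the adjusted post-period comparison already planned. Add a sensitivity analysis that leaves the recruiting encounter out of the pre-utilization covariate.

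The cost is one more abstracted field (source and date) from charts already under review, a few sentences in the SAP, and a probably less favourable pre-to-post figure. The SAP is written in the past tense; if the models have already been run, they need re-running once the field is filled.

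### Poor medication adherence is one route into the programme but is not asked of controls, and no baseline drug or refill status is listed, matched on or modelled, so the HbA1c comparison may be confounded

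*Protocol*

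**What the plan says.** **Entry to the programme.** Besides the general inclusion criteria, which include an A1C of at least 9.0%, the Protocol (III, Inclusion Criteria) asks for "one or more of the following high risk characteristics". Seven are listed. One is "Evidence of low medication adherence as evidenced by no refills since one or more prescribed DM RXs" ran out, judged from the EMR/SureScripts medication list, or any other sign of poor adherence noted by the care team. Patients with a new diagnosis are also eligible.

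**Controls.** The Protocol (III, after the data list) describes them only as randomly selected MedStar patients with elevated A1C. It gives no adherence or other high-risk criterion and no separate data list for them.

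**Data.** The list for patients who complete the programme includes "A1C baseline, at 3 month after baseline visit to assess impact of the pathway", demographics, hypoglycaemic events, a knowledge test, ED and hospital visits, and satisfaction. It has no drug, refill or adherence item.

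**Matching and models.** Pilot patients were "matched to controls at a 1:3 ratio on age, sex, race/ethnicity, insurance group, and baseline A1C" (Protocol, I- Background). The SAP tests outcome differences unadjusted, allowing for matching, and does not name its matching factors. Its HbA1c model by sex names only a sex-by-group interaction. Its one listed covariate set (pre-intervention utilization, baseline HbA1c, age, sex) belongs to the Poisson utilization models.

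**Intervention.** The programme includes "algorithm-driven diabetes medications (DM) titration" and education tailored to adherence deficits (Protocol, I- Background).

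**The concern.** The comparison is not randomised, and the two groups are selected by different rules on a variable that bears on how far HbA1c can fall. Two patients with the same A1C may have it for different reasons: one has stopped taking prescribed drugs or was never prescribed any, while the other is uncontrolled on drugs that are being taken. It is plausible, though the documents do not establish it, that the first has more room to improve once any clinician acts. Matching on baseline A1C, even with age, sex, race/ethnicity and insurance group, balances the level and not the reason for it.

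The Protocol itself says that usual-care physicians act on a markedly raised A1C, and it reports a fall of 1.64 in pilot controls. If lapsed or untreated patients are commoner among programme patients, some of their fall would have happened without the programme yet would be credited to it. The comparison is meant to assess the programme's impact and effectiveness, and manuscripts are planned. Under the plan as written, nobody could show whether such an imbalance exists.

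**Working it through.** **1. The plan's own figure.** The SAP states: "The study was powered to detect a difference of 0.5 in the change in HbA_{1c} with SD=2 with 80% power at alpha=0.05". For this it plans 128 pairs and names the paired t-test. For a two-sided test of that kind (sidedness is not stated), taking SD 2 as the SD of the within-pair difference, the noncentrality is 0.5/2 × √n. Power is 0.798 at 127 pairs and 0.802 at 128, so 128 is reproduced. On the result, the SAP adds: "The study reaches 100% power to detect this observed difference (1.6, SD=2.25, post-hoc) with an alpha level of 0.01". Check: 1.6/2.25 × √128 = 8.05 against a critical value of about 2.6, so power is effectively 100%. The present point changes neither figure. It concerns bias, which sample size does not reduce.

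**2. Where baseline treatment status could be handled.**

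| Place | Drug, refill or adherence item? |
|---|---|
| Programme entry | Yes, one of seven alternatives |
| Control selection | None stated |
| Data list | None |
| Pilot matching factors | None |
| SAP HbA1c models | None |
| SAP utilization covariates | None |

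**3. Bias formula.**

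Bias = (share lapsed or untreated in programme patients − share in controls) × (extra HbA1c fall of such a patient, at equal baseline A1C, under usual care).

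Only the fall that would occur under usual care enters. A restart caused by the programme does not.

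**4. Range.** The documents give neither input. Assumed: share difference 20 to 40 percentage points; extra fall 0.5 to 1.5.

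- Low: 0.20 × 0.5 = 0.10
- Middle: 0.20 × 1.5 = 0.30
- High: 0.40 × 1.5 = 0.60

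Against the planning difference: 0.10/0.5 = 20%; 0.60/0.5 = 120%.
Against the SAP's observed difference: 0.10/1.6 = 6%; 0.60/1.6 = 38%. The high case leaves 1.6 − 0.60 = 1.0.

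If the shares are equal the bias is 0. If controls are lapsed more often by the same margins, it is −0.10 to −0.60 and the programme is understated.

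**5. Could it explain all of 1.6?** The share difference needed is 1.6 divided by the extra fall: 1.6/2 = 80 points, or 1.6/3 = 53 points. At 1.5 it is 107 points, which is impossible.

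**6. Effect on the test.** With no true effect, 128 pairs and SD 2, the chance of a significant result at a nominal 5% is about 9% for a bias of 0.10, 39% for 0.30 and 92% for 0.60.

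**7. Precision of a split.** If 64 of the 128 pairs were analysed alone (an assumed even split), power for 0.5 with SD 2 is about 50%.

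**The case against.** The strongest reply is that getting patients back on treatment is what the programme does. That is right. A reader might infer that any restart of lapsed drugs counted in the HbA1c fall is an error, but the documents do not support this: education targets adherence deficits and drugs are titrated, so a restart the programme brings about is intended effect. Adjusting for restarts after baseline would remove real effect. What remains is baseline imbalance combined with restarts that usual care would have achieved.

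Several other objections stand as limits:

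- Lapsed refills are one of seven alternatives, and the share entering that way is not given.
- Controls are not screened to exclude lapsed patients, so the shares may be similar.
- Lapsed patients may be less likely to resume under usual care, which would shrink or reverse the bias.
- The absence of drug data for controls is an inference from silence, and the SAP does not itemise the patient characteristics it compares.
- The five matching factors are stated for the pilot; those of the SAP analysis are not named.
- In a retrospective chart review the data could still be retrieved, so the gap is not irreparable.

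None of these shows that the groups are balanced on baseline treatment.

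**Conclusion.** The concern holds as possible, unmeasured confounding by baseline treatment status. Direction and size are unknown. Under the assumptions shown the bias is 0.10 to 0.60 HbA1c points, enough to matter against the 0.5 planning difference.

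A reader might go further and infer that the observed 1.6 is an artefact of selection. The documents do not support that: the upper end of the assumed range still leaves 1.0, and removing all of 1.6 would need a share difference of 53 to 80 points together with an extra fall of 3 to 2 points. This is a worthwhile and inexpensive improvement to the analysis, and it does not overturn the result.

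**What to change.** For both groups, abstract three items from the EMR/SureScripts list, as at the baseline A1C date and with the same look-back:

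1. Insulin use (yes/no).
2. Number of glucose-lowering classes.
3. Treatment status: on treatment with current refills; prescribed but lapsed; or no glucose-lowering drug prescribed, including new diagnoses. The third level is needed because a yes/no lapsed field would put untreated patients with those on current treatment.

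Tabulate these by group. Add them as baseline covariates in the HbA1c mixed model and report that estimate beside the unadjusted matched one. Do not adjust for restarts after baseline. Report the programme difference by treatment status descriptively only.

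**Cost.** Three extra fields per chart. For programme patients the list is already consulted at screening; control charts are not described as screened, so theirs would have to be opened for this purpose. A refill-based field cannot reproduce the care team's wider judgement of poor adherence, so some confounding may remain. Estimates by treatment status would be imprecise and would break pairs whose members differ in status.
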